8 PHARMACEUTICAL AND/OR IMAGING AGENT INFORMATION

N/A

9 BIOMARKER, CORRELATIVE, AND SPECIAL STUDIES

9.1 Biomarker Studies

N/A

9.2 Investigational Device Information

N/A

9.3 Laboratory Correlative Studies

Pulmonary Nodule Biopsy

Collection of Specimen(s)

Tissue samples will be obtained using multimodality tools, including cytology brush, fine needle for aspiration, biopsy forceps, and bronchoalveolar lavage at the discretion of the performing provider.

Historically, 4 specimens or passes have been shown to be adequate for optimal diagnostic yield in central lesions (22,23). When the tumor is located on the lateral wall of the airway, biopsy specimens are difficult to obtain using standard forceps. To optimize specimens, use of a spear forceps that has a small needle between the biopsy jaws to anchor into the airway wall is recommended. Additional malignant cells are obtained when bronchial wash is performed after bronchial brushing and bronchial biopsy (24). Most bronchoscopists perform bronchial brushing, biopsy, and washing in that order.

Although, in most cases 4 specimens/passes may be enough to make a diagnosis of lung cancer, they may not provide enough tissue to perform a more detailed molecular analysis. In patients with suspected non-small cell lung cancer (NSCLC), 4 passes may not be enough. Thus, with the use of multiple needle passes and ROSE by proficient endoscopists enough tissue can be aspirated to obtain material suitable for both cytologic diagnosis as well as additional immunohistochemical and molecular testing for EGFR and ALK mutations. Consideration should be given to obtaining up to 6 specimens/passes.

Handling of Specimens(s)

Handling of specimens will be done as stated by the Pathology-laboratory guidelines for ROSE and for further examination.

Shipping of Specimen(s)

N/A

Site(s) Performing Correlative Study

Beth Israel Deaconess Medical Center.

9.4 Special Studies

N/A

10 STUDY CALENDAR

Baseline evaluations (Standard of Care for Bronchoscopy procedures) are to be conducted within 1 week prior to the procedure. Scans and x-rays are usually done ≤ 3 months prior to the start of procedure, this timeframe will be at the discretion of the PI. If the participant's condition is deteriorating, laboratory evaluations should be repeated within 24 hours prior to initiation of the procedure at the discretion of the PI.

Lab tests taken before the procedure are part of the standard of care. Blood collection will not differ from the usual amounts required for conducting the preanesthetic consultation. A negative blood or urine pregnancy test is required prior to performing the procedure as it involves low dose radiation.

Typical follow-up consultations for standard bronchoscopy procedures are done 1 week. If biopsy is benign or non-diagnostic then the patients will be followed at 4 weeks, and 24 weeks after the procedure but may vary depending on the subject's final diagnosis, underline conditions, further treatment, and PI/Investigator preference.

During the follow-up time, subjects will receive phone calls from the study team to check on the subjects well-being and to remind him/her of any future appointments.

11 MEASUREMENT OF EFFECT

N/A

12 DATA REPORTING / REGULATORY REQUIREMENTS

12.1 Data Reporting

To ensure subject privacy, all data collection will be performed in the Chest Disease Center research office. Only authorized BIDMC employees have access to this office. The data collected electronically will be held securely on a secure network drive (RedCap®). No PHI will be used in the analysis or publishing of the data.

12.2 Data Safety Monitoring

Local data and safety monitoring will be conducted in accordance with Beth Israel Deaconess data safety monitoring plan and policies.

12.3 Multi-Center Guidelines

N/A

12.4 Collaborative Agreements Language

N/A

13 STATISTICAL CONSIDERATIONS

Previous studies have shown variable CBCT diagnostic yields, but prospective evidence remains poor. Sobieszczyk et al. published retrospective case series of 22 patients with combination of ENB, R-EBUS, CBCT and TBAT reporting a diagnostic yield of 77.2%. However, authors have not clarified how such yield was calculated. Ali et al. reported prospective case series of 40 patients with combination of ultrathin bronchoscope, ENB and CBCT achieving diagnostic yield of 90% (11). However, the likely explanation for such high yield is inclusion of nodules with bronchus sign only, and inclusion of non-specific inflammation in diagnostic yield calculation. Casal et al. combined thin/ultrathin bronchoscope, R-EBUS and CBCT in a prospective series of 20 patients (19). The median size of the nodules in the series was 21 mm, and diagnostic yield was 70%. In their series non-specific inflammation were considered diagnostic if confirmed by surgical pathology or resolved or improved during follow-up period. Hofenforst-Schmidt et al. published one of the earliest series on CBCT and peripheral pulmonary nodules (25). It was a prospective series of 33 patients divided into subgroups bases on nodule size \leq 20 mm, and $>$ 20 mm. The reported diagnostic yield was 75% in subgroup of nodules \leq 20 mm (mean size 15 mm) and was 67% in subgroup of nodules $>$ 20 mm (mean size 30mm). In 2018, Pritchett et al. published one of the larger retrospective series of 74 patients with 92 nodules combining ENB and CBCT-AF (20). The median lesion size was 16 mm in their series and diagnostic yield of 83.7%.

The overall diagnostic yield of currently available ENB alone is 67% based on meta-analysis of 11 studies (17). We aim to detect an absolute 20% difference between CBCT+NB and NB alone

13.1 Study Design/Endpoints

Primary outcome of diagnostic yield will be determined from the results of NB as compared with CBCT-guided NB. A biopsy that results in a specific diagnosis, either malignant or benign (i.e. granuloma, inflammation, fibrosis, infection) will be assumed to be a true positive with appropriate follow up as indicated for up to 6 months. Atypia or lung parenchyma without pathologic findings on final pathology reads will be considered non-diagnostic. If a nondiagnostic lesion resolved, stayed stable or decreased in size on follow-up CT for at least 6 months after the index procedure then this will be presumed benign and classified as a true negative for the purposes of calculating sensitivity and prevalence of malignancy, as well as for diagnostic accuracy.

Confirmation of the diagnosis by surgery, CT guided TTNA or repeat imaging will be recorded for those patients who have nondiagnostic results from the study procedures. If the subject is referred for surgery, the surgical pathology will be considered the final diagnosis.

If the subject has follow-up imaging that shows a decrease in size or resolution of the nodule, the nodule will be determined to be of benign etiology if the study pathology yields a benign diagnosis (granuloma, inflammation, fibrosis, infection).

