1.1 Study Design

- We propose a prospective, randomized, two- arm, single-center nonblinded, controlled clinical trial to evaluate the diagnostic yield of lung biopsy in NB-alone and CBCT-guided NB.
- Randomization schedule will be determined in advance by computer with the intent of a 1:1 randomization scheme.
- For randomization, Block randomization will be used. The block randomization method is designed to randomize subjects into groups that result in equal sample sizes. This method is used to ensure a balance in sample size across groups over time. This was decided based on the limited access to the Cone Beam room, which is available exclusively once a month (the first Friday of each month).
- All bronchoscopies will be performed under general anesthesia and ROSE will be available upon physician request/preference.
- Radial probe-EBUS and fluoroscopy will be utilized in all cases.
- Tissue samples will be obtained using multimodality tools, including cytology brush, fine needle for aspiration, biopsy forceps, and bronchoalveolar lavage.
- NB procedure will be performed per product instructions and the institution's standard practice.

CBCT-guided NB procedure arm:

Following intubation, an inspiratory breath-hold maneuver with the adjustable pressure limiting (APL) valve set at 20 cm H₂O will be performed by the anesthesiology provider. This mimic the inspiratory

breath hold done during a CT scan. During the breath-hold maneuver, CBCT will be performed. A dedicated arm attached to the bronchoscopy cart will be utilized to hold the bronchoscope in position so that the operators can leave the room during CBCT scan. Lung nodules will be highlighted using available software (OncoSuite; Philips) during a process known as segmentation. A bronchoscope will be introduced into the airway and then using NB to navigate to the lesion. Nodule segmentation will be visualized in an overlay with live fluoroscopy. Geometric correspondence of augmented fluoroscopy (AF) will be maintained throughout the case while manipulating C-arm angulation, table position, and image-zoom settings. Final catheter position will then be verified in multiple planes with AF. Additional CBCT scans will be acquired when deemed necessary.

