13.5 Analysis of Primary Endpoints

The overall diagnostic yield will be calculated by adding the number of true positives (TP) for both malignancy and benign disease in the numerator and dividing by the total number of procedures performed for each arm of the study.

Proportions will be compared with the Chi-Square Test as this test is equivalent to the z-test of two proportions (26). A p-value <0.05 will be considered as statistically significant.

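### No masking is specified for the final pathology read or its coding, although part of the primary endpoint rests on a judgement between benign change and non-diagnostic tissue

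*Combined protocol and SAP*

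**What the plan says.** Section 1.1 describes a "single-center nonblinded, controlled clinical trial". It names no party who is to be masked.

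Section 13.1 defines success: "A biopsy that results in a specific diagnosis, either malignant or benign (i.e. granuloma, inflammation, fibrosis, infection) will be assumed to be a true positive". It defines failure in the next sentence: "Atypia or lung parenchyma without pathologic findings on final pathology reads will be considered non-diagnostic". Section 13.5 carries this into the primary endpoint by "adding the number of true positives (TP) for both malignancy and benign disease in the numerator", over all procedures performed in the arm.

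On how specimens reach the reader, section 9.3 says only: "Handling of specimens will be done as stated by the Pathology-laboratory guidelines for ROSE and for further examination". Section 13.7.2, on evaluation of the primary efficacy endpoint, is marked as not applicable. No section says what the requisition contains, who assigns the diagnostic or non-diagnostic code, or whether that person knows the arm.

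Section 13 recognises that this category is sensitive. In discussing a prospective series of 40 patients with a 90% yield, it gives as part of the likely explanation "inclusion of non-specific inflammation in diagnostic yield calculation". It also notes that a series of 20 patients counted such findings only after surgical confirmation, or after resolution or improvement in follow-up.

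**The concern.** A small biopsy showing mild inflammatory or fibrotic change can reasonably be reported as such, or as lung tissue with nothing of note. Under section 13.1 the first report scores as a success and the second as a failure. The operator necessarily knows the arm. If the reader or coder also knows it, borderline specimens may be called differently in the two arms. That would bias the difference in yield directly, and a larger sample would not remove it.

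Follow-up is only a partial check. Section 13.1 treats a specific benign result as a true positive by assumption, with follow-up where indicated, and section 5.6 makes the 24-week follow-up permissive. The sentence in section 13.1 on recording confirmation by surgery, transthoracic aspiration or repeat imaging applies to patients whose study result was non-diagnostic. A borderline specimen called inflammation would fall outside it.

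**Working it through.** **Inputs from the documents.** Control yield 67% and target difference 20 points (section 13); 68 per arm, two-sided alpha 0.05, 80% power, uncorrected chi-squared test (section 13.2).

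**The plan's own figure.** With p1 = 0.67, p2 = 0.87 and mean 0.77,

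n = [1.960·√(2·0.77·0.23) + 0.842·√(0.67·0.33 + 0.87·0.13)]² / 0.20² = [1.960·0.595 + 0.842·0.578]² / 0.04 ≈ 68.3.

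That is 69 per arm when rounded up, against 68 in the plan; power at 68 per arm is 79.8%. The sample size is not in dispute, and masking does not alter it.

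**Assumed input.** Let f be the share of the CBCT arm's non-diagnostic reads that is called inflammation or fibrosis because the arm is known, with no shift in the control arm. The documents give no value for f, so a range is shown.

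**Formulas.** With a true yield of 67% in both arms, the observed CBCT yield is 0.67 + 0.33·f. The expected number of extra diagnostic reads is 68·0.33·f = 22.44·f. The rejection rate is the sum of exact binomial probabilities over all pairs of counts (68 per arm) for which the uncorrected chi-squared test gives p < 0.05.

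| f | Extra reads of 68 | Observed CBCT yield | Two-sided rejection rate | Part favouring CBCT |
|---|---|---|---|---|
| 0 | 0 | 67.0% | 5.2% | 2.6% |
| 5% | 1.1 | 68.7% | 5.7% | 4.1% |
| 10% | 2.2 | 70.3% | 7.2% | 6.3% |
| 20% | 4.5 | 73.6% | 13.6% | 13.3% |
| 30% | 6.7 | 76.9% | 25.1% | 25.1% |

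**If only some non-diagnostic specimens are borderline.** Suppose half are. A 20% shift among those is f = 10% overall (7.2%), and a 30% shift is f = 15% overall (9.8%).

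**If there is a real but smaller gain.** With 67% against 77%, the chance of significance is 25.6% with no shift. It is 36.8% at f = 10% (observed yield 0.77 + 0.23·0.10 = 79.3%) and 50.0% at f = 20% (81.6%).

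**In counts.** Starting from 46 diagnostic reads in each arm, ten reclassified reads in one arm are needed to reach significance. With 46 against 56 the pooled proportion is 102/136 = 0.75, and z = (10/68) / √(0.75·0.25·2/68) = 0.1471/0.0743 = 1.98. With nine, z = 1.77.

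**The case against.** The strongest objection is that silence is not evidence. A reader might infer from the nonblinded label that the pathologists know the arm. The documents do not say so: they describe neither the requisition nor what accompanies the specimen, and they defer to laboratory guidelines that are not reproduced. What can be said is that no masking is specified. This part of the objection stands, and the point is worded accordingly.

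A second objection is that a small shift does little. This also stands: at 5% the rejection rate moves from 5.2% to 5.7%, and at 10% to 7.2%. The larger figures need about 4.5 to 6.7 specimens to be upgraded, all in one arm. Malignant, granuloma and infection reads also count toward yield and are less open to this judgement. Only the benign/non-diagnostic boundary is clearly exposed, and its share of the endpoint is unknown.

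A third is that masking is not the only protection. Narrowing the benign categories in section 13.1 would remove much of the subjective boundary, and surgical pathology, where surgery takes place, becomes the final diagnosis. Both are true. It would therefore be wrong to call the final read the only place where the outcome can be protected. Masking has the advantage of leaving the endpoint definition as it is, but it does not settle whether non-specific inflammation should count.

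A fourth is that masking may leak. Section 1.1 says the Cone Beam room is available on one day a month, the first Friday, and the documents do not say when control procedures take place. If they fall on other days, the date reveals the arm. This limits the masking of the reader; for the coder it can be met by removing the date.

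**Conclusion.** The point holds as a gap with a cheap remedy. A nonblinded trial has a primary endpoint that depends in part on judgement, and the plan specifies no masking for the final read or its coding. Section 13 itself regards the category at issue as a likely reason for a high yield elsewhere.

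The effect on the false-positive rate runs from negligible (5.7% against 5.2%) to serious (25.1%) over shifts of 5% to 30%. This rests on three assumptions: a true yield of 67% in both arms, a shift confined to the CBCT arm, and a range of f that the documents neither support nor exclude. It shows what could happen, not what will. A reader might go further and infer that the comparison is biased, or that readers are known to be aware of the arm; the documents support neither.

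**What to change.** Add to section 13.1:

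- Requisitions and labels for the routine final read omit the arm, the room and any mention of CBCT use.
- The diagnostic or non-diagnostic code is assigned by existing staff not involved in the procedure, from copies of the final reports with the arm, room, CBCT use and procedure date removed.
- Coding is completed before the codes are linked to the allocation list.

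The cost is a requisition template and one coding step. That no additional reader is needed is an inference: section 13.1 already relies on a final pathology read, and the same read can be made from a requisition without the arm. Sample size, test, endpoint definition and patient procedures are unchanged.

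The protection of the reader is partial in two situations, and the protocol should say so: where the person who gave the on-site evaluation (optional under section 1.1) also signs the final report, and where the specimen date reveals the arm because of the Cone Beam room schedule. The coding step still adds protection in both.

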If a non-diagnostic lesion resolved, stayed stable or decreased in size on follow-up CT for at least 6 months after the index procedure then this will be as presumed benign and classified as a true negative for the purposes of calculating sensitivity and prevalence of malignancy, as well as for diagnostic accuracy.

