3.3 Eligibility Criteria

- 1) Patients ≥ 18 years old.
- 2) Patients with lesions having an intermediate pre-test probability of malignancy (pCA, 0.05 to 0.65) as determined by Swensen-Mayo nodule risk calculator and in whom bronchoscopic biopsy was determined to be the next best treatment step by the treating pulmonologists
- 3) Patients with higher risk lesions (pCA > 0.65) in need of a diagnosis for nonsurgical treatment or prior to surgery.
- 4) Patients are willing and able to provide informed consent.

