For patients that continue in the study due to a benign or non-diagnostic biopsy, information related to any additional procedural complications (i.e. pneumothorax or pneumonia) will be collected.

Post-procedure (up to 180 days) Assessment

For patients that continue in the study due to a benign or non-diagnostic biopsy. Pathology and disease information will be obtained from any additional diagnostic assessments, interventions or treatments associated with the study related nodule(s).

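### The true-negative rule in 13.1 looks only at CT size course, so a missed cancer treated without surgery and not growing at 6 months is scored benign

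*Combined protocol and SAP*

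**What the plan says.** Section 13.1 sets the imaging rule: "If a nondiagnostic lesion resolved, stayed stable or decreased in size on follow-up CT for at least 6 months after the index procedure", the lesion is presumed benign and "classified as a true negative for the purposes of calculating sensitivity and prevalence of malignancy, as well as for diagnostic accuracy". Section 1.1 states the same rule. Size course is the only condition in either place.

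On competing evidence, 13.1 is explicit for one source: "If the subject is referred for surgery, the surgical pathology will be considered the final diagnosis". For patients with a nondiagnostic study procedure, confirmation by surgery, CT-guided transthoracic needle aspiration (TTNA) or repeat imaging is to be recorded, but TTNA is given no stated rank against the CT rule.

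Non-surgical treatment is foreseen. Section 3.3 admits "Patients with higher risk lesions (pCA > 0.65) in need of a diagnosis for nonsurgical treatment or prior to surgery". Section 3.6 collects later pathology, interventions and treatments of the nodule up to 180 days when the biopsy was benign or nondiagnostic.

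Two provisions touch the problem. Exclusion 1 in 3.4 covers a predetermined plan for stereotactic radiation (SBRT) after a nondiagnostic procedure, for outer-third nodules. Section 5.7 repeats this and adds nodules that cannot be reached percutaneously.

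**The concern.** Lack of growth over 6 months suggests benign disease only if nothing was done to the lesion. After radiation or systemic treatment, a stable or smaller lesion is equally what a treated cancer would show. The rule as written does not separate the two.

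Each such lesion is a false negative that becomes a true negative. That removes it from the denominator of sensitivity, adds it to the correct calls in accuracy, and takes it out of the count of malignant lesions. Since this can happen only after a nondiagnostic biopsy, an arm with more nondiagnostic biopsies is more exposed.

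**Working it through.** **1. Reading the rule on three records.** Each starts with a nondiagnostic study biopsy and ends stable or smaller on CT at 6 months.

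- *A: later TTNA malignant, then non-surgical treatment.* The CT rule, taken alone, gives true negative. The TTNA is recorded as confirmation, but nothing says which prevails.
- *B: treated as cancer without tissue, decided after the result.* The CT rule gives true negative, and nothing in 13.1 competes with it. Sections 3.4 and 5.7 do not apply because the plan was not predetermined.
- *C: untreated.* True negative, as intended.

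**2. The plan's own figures.** Section 13 gives 67% for navigation alone and a 20-point target, hence 87%. Section 13.2 gives 68 per arm, two-sided 0.05, 80% power and an uncorrected chi-squared test. With mean proportion 0.77:

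n = [1.960·√(2·0.77·0.23) + 0.842·√(0.67·0.33 + 0.87·0.13)]² / 0.20² = 68.3, so 69 per arm; power at 68 is 79.8%.

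The stated 68 is reproduced to within one patient, so 67% v 87% is a fair reading of the design.

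**3. Lesions exposed to the rule.** Nondiagnostic = 68 × (1 − yield): 68 × 0.33 = 22.4 with NB alone and 68 × 0.13 = 8.8 with CBCT, a ratio of 2.5. With equal yields the expected counts would be equal.

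**4. Illustrative size.** Three inputs are assumptions, not in the documents: 60% of lesions malignant; half of nondiagnostic lesions malignant; and a share f of those missed cancers treated non-surgically and not growing at 6 months. The plan gives no formula for sensitivity, so I take true positives / (true positives + false negatives) for malignancy.

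- Malignant per arm: 0.6 × 68 = 40.8.
- Missed: 0.5 × 22.44 = 11.22 and 0.5 × 8.84 = 4.42.
- Detected: 40.8 − missed = 29.58 and 36.38.
- Misclassified: k = f × missed. Scored sensitivity = detected / (40.8 − k).

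| f | k, NB | k, CBCT | Sensitivity, NB | Sensitivity, CBCT | Difference (points) |
|---|---|---|---|---|---|
| 0 (correct) | 0 | 0 | 72.5% | 89.2% | 16.7 |
| 10% | 1.1 | 0.4 | 74.6% | 90.1% | 15.6 |
| 30% | 3.4 | 1.3 | 79.0% | 92.2% | 13.1 |
| 40% | 4.5 | 1.8 | 81.5% | 93.2% | 11.7 |

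At f = 30%, accuracy rises by k/68, about 5 points (NB) and 2 points (CBCT). Apparent prevalence, (40.8 − k)/68, falls from 60% to about 55% and 58%.

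**5. A different assumption.** Suppose instead that yield is the same in malignant and benign nodules. True sensitivity is then 67% v 87%, and scored sensitivity is y / [y + (1 − y)(1 − f)]: 69.3% v 88.1% at f = 10%, 74.4% v 90.5% at 30%, 80.2% v 93.0% at 50%. The 20-point difference becomes 18.9, 16.2 and 12.8. At f = 30%, misclassified lesions number 2.7 v 1.1 if prevalence is 40% and 5.4 v 2.1 if it is 80%. The direction is the same; the size moves.

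**6. Would dropping the treated lesions be enough?** No. Removing k lesions from the false negatives has the same effect on sensitivity whether they become true negatives or are excluded. At f = 30%, 29.58/(40.8 − 3.37) = 79.0% and 36.38/(40.8 − 1.33) = 92.2%, exactly the inflated values. Prevalence is only partly restored: 37.43/64.63 = 57.9% and 39.47/66.67 = 59.2%.

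**The case against.** The strongest reply is that a sensible analyst would never score a TTNA-proven cancer as benign. The CT rule is a presumption for lesions without tissue; 13.1 goes on to name TTNA beside surgery as confirmation, and 5.7 treats tissue before SBRT as the expected route. This largely stands for record A: a reader might infer that such cancers will be scored benign, but the documents show only that precedence is unstated. Stating it still matters, because 1.1 makes the trial nonblinded and case-by-case judgement would be made knowing the arm.

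For record B, the reply is that 3.4 and 5.7 already handle SBRT without tissue, and that the 3.3 group needs a diagnosis before non-surgical treatment. Both points narrow the exposure, and the documents give no frequency for it. Neither covers treatment decided after the result.

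The reply is also right that these measures are peripheral. Sensitivity, prevalence and accuracy are not among the objectives in 1.2 and 1.3, and 13.6 plans no between-arm test of them. The plan nevertheless writes this rule expressly to calculate them.

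**Conclusion.** The point holds as a gap in an outcome definition. Followed as written, the rule scores a missed cancer as benign when it has been treated non-surgically and has not grown. The clearest case is treatment without tissue decided after the result. Under the assumptions in step 4, sensitivity with NB alone is inflated by about 2 to 9 points for f of 10% to 40%. These sizes are illustrative: three inputs come from outside the documents, and the split between records A and B is unknown.

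Three stronger readings are not supported.

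- *That the primary result is biased.* Section 13.5 divides true positives by all procedures, so reclassifying a nondiagnostic lesion changes neither term.
- *That NB alone is always flattered.* This holds if yields differ as the plan assumes, and it then narrows any between-arm contrast in these measures. With equal yields the expected error would not differ by arm.
- *That benign reads carry the same error into the primary numerator.* The last paragraph of 13.1, which settles a shrinking or vanished nodule as benign when the study pathology is benign too, likewise lacks an untreated condition. However, the documents show no route by which a benign-read lesion goes on to anti-cancer treatment, and no size can be given.

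**What to change.** In 13.1 and 1.1, state that:

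1. any later malignant tissue result, from surgery, TTNA or another sample, overrides the CT rule;
2. the CT rule applies only to lesions with no anti-cancer treatment before the classifying CT;
3. a lesion treated as cancer without tissue is never a true negative. Count it as presumed malignant, hence a false negative, in the main sensitivity, prevalence and accuracy figures, and report the all-benign bound alongside. Do not drop it, for the reason in step 6.

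Adding the untreated condition to the benign-read paragraph is an optional edit for consistency.

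The cost is a few sentences. Section 3.6 already collects later pathology and treatment; if a classifying CT falls after day 180, collection should run to the date of that CT. The downside is that accuracy figures become slightly less favourable, and if some lesions treated without tissue were in fact benign, the main figures will understate sensitivity, which is why the bound is needed. The sample size, the primary test and patient care do not change.
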